5.1.2 AE date imputation

Table 5-1 Imputation of start date

Missing Element	Rule
day, month, and year	
• No imputation will be done for completely missing dates
day, month	
• If available year = year of study treatment start date then
◦ If stop date contains a full date and stop date is earlier than study treatment start date then set start date = 01JanYYYY
◦ Else set start date = study treatment start date.• If available year > year of study treatment start date then 01JanYYYY• If available year < year of study treatment start date then 01JulYYYY

Missing Element	Rule
day	
 • If available month and year = month and year of study treatment start date then 
 ◦ If stop date contains a full date and stop date is earlier than study treatment start date then set start date = 01MONYYYY. ◦ Else set start date = study treatment start date. • If available month and year > month and year of study treatment start date then 01MONYYYY • If available month and year < month year of study treatment start date then 15MONYYYY

Table 5-2 Imputation of end date

Missing Element	Rule (*=last treatment date plus 105 days not > (death date, cut-off date, withdrawal of consent date))
day, month, and year	
 • Completely missing end dates (incl. ongoing events) will be imputed by the end date of the on-treatment period
day, month	
 • If partial end date contains year only, set end date = earliest of 31DecYYYY or end date of the on-treatment period
day	
 • If partial end date contains month and year, set end date = earliest of last day of the month or end date of the on-treatment period

Any AEs with partial/missing dates will be displayed as such in the data listings.

Any AEs which are continuing as per data cut-off will be shown as 'ongoing' rather than the end date provided.

For AEs with start date before or on the cut-off date and end date after the cut-off date, the outcome will be reported as unknown.

5.1.3 Concomitant medication date imputation

Table 5-3 Imputation of start dates

Missing Element	Rule
day, month, and year	
 • No imputation will be done for completely missing dates
day, month	
 • If available year = year of study treatment start date then 
 ◦ If stop date contains a full date and stop date is earlier than study treatment start date then set start date = 01JanYYYY ◦ Else set start date = study treatment start date. • If available year > year of study treatment start date then 01JanYYYY

Missing Element	Rule
	
 • If available year < year of study treatment start date then 01JulYYYY
day	
 • If available month and year = month and year of study treatment start date then 
 ◦ If stop date contains a full date and stop date is earlier than study treatment start date then set start date= 01MONYYYY. ◦ Else set start date = study treatment start date. • If available month and year > month and year of study treatment start date then 01MONYYYY • If available month and year < month year of study treatment start date then 15MONYYYY

Table 5-4 Imputation of end dates

Missing Element	Rule (*=last treatment date plus 105 days not > (death date, cut-off date, withdrawal of consent date))
day, month, and year	
 • Completely missing end dates (incl. ongoing events) will be imputed by the end date of the on-treatment period
day, month	
 • If partial end date contains year only, set end date = earliest of 31DecYYYY or end date of the on-treatment period
day	
 • If partial end date contains month and year, set end date = earliest of last day of the month or end date of the on-treatment period

Any concomitant medications with partial/missing dates will be displayed as such in the data listings.

Any concomitant medications which are continuing as per data cut-off will be shown as 'ongoing' rather than the end date provided.

5.1.3.1 Prior therapies date imputation

Refer [Section 5.1.3](#)

5.1.3.2 Post therapies date imputation

Refer [Section 5.1.3](#)

5.1.3.3 Other imputations

Table 5-5 Imputation of start dates assessments (laboratory, ECG, vital signs)

Missing Element	Rule
day, month, and year	
• No imputation will be done for completely missing dates
day, month	
• If available year = year of study treatment start date then
◦ If stop date contains a full date and stop date is earlier than study treatment start date then set start date = 01JanYYYY
◦ Else set start date = study treatment start date.• If available year > year of study treatment start date then 01JanYYYY• If available year < year of study treatment start date then 01JulYYYY
day	
• If available month and year = month and year of study treatment start date then
◦ If stop date contains a full date and stop date is earlier than study treatment start date then set start date= 01MONYYYY
◦ Else set start date = study treatment start date.• If available month and year > month and year of study treatment start date then 01MONYYYY• If available month and year < month year of study treatment start date then 15MONYYYY

5.2 AEs coding/grading

Adverse events are coded using the Medical dictionary for regulatory activities (MedDRA) terminology.

Note: The latest available MedDRA version at the time of the analyses should be used. The MedDRA version used should be specified in the footnote of relevant tables. AEs will be assessed according to the Common Terminology Criteria for Adverse Events (CTCAE) version 5.0. The CTCAE represents a comprehensive grading system for reporting the acute and late effects of cancer treatments. CTCAE grading is by definition a 5-point scale generally corresponding to mild, moderate, severe, life threatening, and death. This grading system inherently places a value on the importance of an event, although there is not necessarily proportionality among grades (a grade 2 is not necessarily twice as bad as a grade 1).

5.3 Laboratory parameters derivations

Grade categorization of lab values will be assigned programmatically as per NCI Common Terminology Criteria for Adverse Events (CTCAE) version 5.0. The calculation of CTCAE grades will be based on the observed laboratory values only, clinical assessments will not be taken into account. The criteria to assign CTCAE grades are given in the Novartis internal

criteria for CTCAE grading of laboratory parameters. The latest available version of the document based on the underlying CTCAE version 5.0 at the time of analysis will be used.

For laboratory tests where grades are not defined by CTCAE version 5.0, results will be graded by the low/normal/high classifications based on laboratory normal ranges.

A severity grade of 0 will be assigned for all non-missing lab values not graded as 1 or higher. Grade 5 will not be used. For laboratory tests that are graded for both low and high values, summaries will be done separately and labelled by direction, e.g., sodium will be summarized as hyponatremia and hypernatremia.

Imputation Rules

CTCAE grading for blood differentials is based on absolute values. However, this data may not be reported as absolute counts but rather as percentage of white blood cells (WBC).

If laboratory values are provided as ' $<X$ ' (i.e. below limit of detection) or ' $>X$ ', prior to conversion of laboratory values to SI unit, these numeric values are set to X.

The following rules will be applied to derive the WBC differential counts when only percentages are available for a xxx differential

$$\text{xxx count} = (\text{WBC count}) * (\text{xxx \%value} / 100)$$

Further derivation of laboratory parameters might be required for CTCAE grading. For instance, corrected calcium can be derived using the reported total calcium value and albumin at the same assessment using the following formula:

$$\text{Corrected Calcium (mg/dL)} = \text{Calcium (mg/dL)} - 0.8 [\text{Albumin (g/dL)} - 4]$$

In order to apply the above formula, albumin values in g/L will be converted to g/dL by multiplying by 0.1, calcium values in mmol/L will be converted to mg/dL by dividing by 0.2495. For calculation of laboratory CTCAE grades 0 and 1, the normal range for derived corrected calcium is set to the same limits (in mg/dL) as for calcium.

CTCAE grades for the derived absolute WBC differential counts (neutrophils, lymphocytes) and corrected calcium will be assigned as described above for grading

5.4 Statistical models

5.4.1 Analysis supporting primary objective(s)

Primary analysis

Wilcoxon signed rank test

The SAS procedure PROC UNIVARIATE will be used to perform Wilcoxon signed-rank test.

Hodges-Lehmann Estimation

The SAS procedure PROC NPAR1WAY will be used to compute the Hodges-Lehmann estimate.

Handling of missing data

Generating the multiple imputation

The missing values will be imputed for the primary analysis.

- To fill in the missing values (i.e. number of priapic events by 26 weeks), generate Poisson distributed random variables with a rate parameter based on the same effect as observed data. Compute 1000 such complete datasets. Use seed 10105.
- Each datasets will be analyzed using the same method as described in primary analysis.

Analyzing the imputed data

- The resulting estimates and standard errors will be combined using Rubin's rule ([Barnard J and Rubin DB 1999](#)), by the SAS procedure MIANALYZE.

Tipping point analysis for priapic events by 26 weeks

As a sensitivity analysis to evaluate the impact of missing data, a tipping point analysis will be performed for the primary endpoint.

The primary endpoint will be re-analyzed on the delta-adjusted datasets to see if the conclusions change. If not, a larger delta is chosen and the process will be repeated until the conclusion is overturned. The tipping point is the delta value which will cause the primary endpoint to be no longer statistically significant. A series of analyses on a range of delta values (i.e., 1,2,3,.....) will be performed to find the tipping point.

For each delta value, the following steps will be performed.

1. Impute the missing values (i.e. number of priapic events by 26 weeks) by generating Poisson distributed random variables with a rate parameter based on the same effect as observed data. Use seed 10105.
2. After the imputation obtained in above step, make the imputed value worse by a value of delta (i.e., add delta to the imputed value). Note: delta = 0 represents the standard missing at random (MAR).
3. The final imputed delta-adjusted dataset where all missing values are filled, will be analyzed using method as described in the primary analysis.
4. The results from the 1000 delta-adjusted datasets will then be combined using Rubin's rule. If the combined results does not change the conclusion (i.e., if percentage reduction in events is $\geq 25\%$ statistically significant), a larger delta will be chosen and Steps 1-4 will be repeated using the datasets from Step 1 until the tipping point is found (when $p > 0.05$).

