#### **4.3 Rationale for choice of control drugs**

This is a single arm study. Therefore, no control group will be assigned.

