### **6.3.2 Treatment assignment, randomization**

This is a single arm study. Therefore, no randomization will be performed in this study.

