1.2.1 Primary estimand(s)

The estimand is the precise description of the treatment effect and reflects strategies to address events occurring during trial conduct which could impact the interpretation of the trial results (e.g. premature discontinuation of treatment).

The primary clinical question of interest is: What is the effect of crizanlizumab on reduction from baseline period in priapic events, by week 26?

The primary estimand is described by the following attributes:

1. Population: Sickle Cell Disease patients with priapism.
2. Endpoint: Percent reduction from baseline period in priapic events (priapism defined as unwanted, or painful erection lasting at least 60 min self-reported) by 26 weeks
3. Treatment of interest: Investigational drug will be a crizanlizumab solution provided every 4 weeks with an additional loading dose 2 weeks after the first dosing.
4. List of intercurrent events:
 - a) Treatment discontinuation.
 - b) Initiation or discontinuation of HU/HC or l-Glutamine (or other therapies to treat SCD and or to prevent/reduce VOCs such as voxelotor and erythropoietin) or of prophylactic treatment for priapism.
 - c) Intake of analgesic (including opioids) or ad hoc transfusions administered temporarily.

5. The summary measure: Median percentage change from baseline period in priapic events (priapism defined as unwanted, or painful erection lasting at least 60 min self-reported) by 26 weeks

Handling of intercurrent events is discussed in [Section 2.5.3](#)

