2.5.2 Statistical hypothesis, model, and method of analysis

It is expected that crizanlizumab treatment reduces priapic events by at least 25% in SCD subjects with priapism.

Demonstration of significant percent reduction from baseline in priapic events will be evaluated using following hypothesis:

$H_0: p < 0.25$, where p is the percent reduction in priapic events by 26 weeks.

$H_1: p \geq 0.25$, where p is the percent reduction in priapic events by 26 weeks.

If the above null hypothesis is rejected, significant reduction in priapic events will be demonstrated statistically.

Assuming uniformity in the occurrence of priapic events before exposure to crizanlizumab treatment, baseline will be adjusted for 26 weeks for analysis purpose.

Baseline (adjusted for 26 weeks): Number of priapic events in 12 weeks screening period * (26/12) and percentage change from baseline = (Post baseline value –Baseline (adjusted to 26 weeks) value) * 100 / Baseline (adjusted to 26 weeks) value.

Percentage reduction from baseline is the negative percentage change from baseline.

Percent reduction from baseline in priapic events will be tested using a non-parametric test (i.e., Wilcoxon's Sign Rank test) and p-value will be reported. The study would be declared a success, if percentage reduction in events is $\geq 25\%$ and $p < 0.05$ is obtained from Wilcoxon's Sign Rank test.

Hodges-Lehmann estimate of median percent reduction in priapic events will also be reported, along with corresponding 95% confidence intervals.

Number of priapic events will be summarized at baseline (adjusted for 26 weeks) and by Week 26, and percent reduction from adjusted baseline by Week 26 will be summarized by n, mean, standard deviation (SD), lower quartile (Q1), median, upper quartile (Q3), minimum and maximum.

Graphical representation of percentage reduction, through box plot or bar graph or waterfall plot, will be performed as appropriate by 26 weeks.

In addition, subgroup analysis of the primary endpoint will be performed based on the number of priapic events categories (i.e. <7, 7 - 13, 14 - 21, \geq 22) at baseline (12 weeks) and baseline (adjusted for 26 weeks). Additional analyses of the primary endpoint will also be performed for the subgroups of subjects with stuttering and acute priapism. Summary statistics for percentage reduction by 26 weeks will be presented for each subgroup.

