2.13 Interim analysis

A formal interim analysis for this study is not planned and shall not be performed. For publication purposes, only descriptive data will be reported, as needed. Any decision on study continuation will not be based on these reports, as such no alpha adjustment will be needed.

The primary analysis of the study will be performed after the last subject has completed Week 26 visit or discontinued earlier. For this analysis, all subjects will have completed the assessments related to the primary, secondary [REDACTED] objectives including all variables outlined up to Week 26 and all available visit-based safety assessments. Separate SAP documentation will be prepared for this primary analysis if applicable.

3 Sample size calculation

A total of 34 evaluable subjects is required for the study to have approximately 80% power to detect at least 25% reduction in rates of priapic events (defined as an unwanted erection lasting at least 60 min reported via daily diary tool) with a mean baseline priapism event rate of 10.0 and standard deviation of the difference of 5.0, by 26 weeks.

The calculations were based on simulation with 5,000 repetitions (from Poisson distribution) using one-sample Wilcoxon's Signed-Rank Test and 2-sided $\alpha=0.05$.

Retaining the same above assumptions, robustness of the estimated sample size was also validated using a one-sample t test.

Assuming a 5% dropout rate, approximately 36 subjects will be enrolled in the study.

Recruitment of the required number of subjects with priapism will be challenging as the incidence of priapic events are sporadic and varies over time intervals. Also, in the absence of relevant clinical data on priapism, the expected reduction and higher variability in events rates have been conservatively assumed. The above expected 25% reduction in rates of priapic events from baseline is based on medical expert opinion and feedback. L-glutamine (EndariTM) was approved by the US FDA in July 2017 for the reduction of vaso-occlusive crises (VOCs), based on a 25% reduction. Since priapism is also considered to be a complicated VOC, the assumption was that the relative risk reduction of 25% (approved for VOC events), would be similar for priapism.

4 Change to protocol specified analyses

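### SAP 5.4.1 assigns a one-sample Hodges-Lehmann estimate to a two-group procedure and gives no input layout; neither workable layout yields the promised estimate and interval

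*SAP*

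**What the plan says.** Each subject is compared with himself. SAP 2.5.2 scales his 12-week screening count by 26/12, compares his Week 26 count with that figure, and so obtains one percent reduction per subject. On that variable, "Hodges-Lehmann estimate of median percent reduction in priapic events will also be reported, along with corresponding 95% confidence intervals". The primary estimand in SAP 1.2.1 has the same target: "The summary measure: Median percentage change from baseline period in priapic events". There is one arm (Protocol 4.3): "This is a single arm study. Therefore, no control group will be assigned".

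The test is one-sample throughout. The sample size in SAP section 3 was simulated "using one-sample Wilcoxon's Signed-Rank Test and 2-sided" alpha of 0.05, and SAP 5.4.1 gives the matching software: "The SAS procedure PROC UNIVARIATE will be used to perform Wilcoxon signed-rank test". For the estimate, the same section says: "The SAS procedure PROC NPAR1WAY will be used to compute the Hodges-Lehmann estimate". It names no class variable, data layout or code. SAP section 4, which lists changes to the protocol analyses, repeats that the estimate will be reported and does not mention the procedure.

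**The concern.** PROC NPAR1WAY works on a one-way layout, and its Hodges-Lehmann output is a location shift between two classes. This trial has no second class. A programmer who follows SAP 5.4.1 literally must create one, and the choice decides the unit, the pairing and the interval. At stake is the effect estimate and interval printed beside the primary p-value. They could be on a different scale from the endpoint, or have an interval that is not derived from the planned test and can disagree with it.

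**Working it through.** **1. Reproduce the plan's own figure.** Inputs from SAP section 3: mean baseline rate 10.0, reduction 25% (10.0 × 0.25 = 2.5 events), SD of the difference 5.0, two-sided alpha 0.05, power about 80%.

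- Normal approximation: n = ((1.960 + 0.842) × 5.0 / 2.5)² = 5.604² = 31.4, so 32.
- One-sample t test at n = 34: power 0.808.
- Signed-rank simulation (5,000 runs, n = 34): power 0.795 with overdispersed counts whose difference has SD 5.0, and 0.778 with normal differences.
- Dropout: 34 / 0.95 = 35.8, so 36.

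The stated 34 and 36 follow from one-sample, paired inputs.

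**2. The promised quantity.** For subject i, let B be the 12-week count × 26/12, Y the Week 26 count, and d = 100 × (B − Y) / B. The one-sample Hodges-Lehmann estimate is the median of all averages (d_i + d_j)/2 with i ≤ j. At n = 34 there are 34 × 35 / 2 = 595 of them. The 95% limits lie at rank n(n+1)/4 − 1.96 × √(n(n+1)(2n+1)/24) = 297.5 − 1.96 × 58.49 = 182.9, that is, the 183rd value from each end.

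**3. Layout A: baseline and Week 26 counts as two classes.** The estimate is the median of the 34 × 34 = 1,156 cross-differences. It is in events, and the pairing is lost. Its width relative to the paired count interval depends on the within-subject correlation, which the documents do not give. With normal data at the planning figures (difference 2.5, SD of difference 5.0, n = 34), the paired interval averages about 3.6 events:

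| Assumed correlation | Unpaired width (events) | Ratio to paired | Theory 1/√(1−ρ) |
|---|---|---|---|
| 0 | 3.5 | 0.98 | 1.00 |
| 0.3 | 4.2 | 1.17 | 1.20 |
| 0.5 | 4.9 | 1.38 | 1.41 |
| 0.7 | 6.3 | 1.77 | 1.83 |

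The next table simulates trials with n = 34, a true reduction of 25%, at least 3 screening events, and counts scaled by 26/12. The rates and the gamma variation are assumptions. Entries are the ratio of the unpaired to the paired count interval width:

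| Mean 26-week rate | No between-subject variation | Gamma k=4 | Gamma k=2 |
|---|---|---|---|
| 10 | 0.96 | 1.28 | 1.44 |
| 15 | 0.99 | 1.45 | 1.65 |
| 20 | 0.98 | 1.62 | 1.83 |

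Over these settings the unpaired interval excludes zero in about 40% to 98% of trials. In the worst of them (mean 20, k=2), the paired count interval does so in about 98%.

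**4. Layout B: percent reductions against 34 zeros.** Each d appears 34 times among the 1,156 differences, so the estimate is the plain sample median. In the simulations this was about 2 to 4 percentage points above the one-sample Hodges-Lehmann value. The limits lie at rank 34²/2 − 1.96 × √(34 × 34 × 69 / 12) = 578 − 1.96 × 81.53 = 418.2. Since 418 / 34 = 12.3, this is the 13th ordered percent reduction from each end. Coverage of the median is 1 − 2 × P(Binomial(34, 0.5) ≤ 12) = 0.88, not 0.95. The 0.88 assumes that the dummy class has as many zeros as there are subjects.

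**5. Ten invented subjects, for illustration only.** Screening counts 3, 4, 5, 6, 8, 10, 12, 15, 20, 30; Week 26 counts 2, 9, 6, 13, 8, 20, 14, 30, 22, 60.

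| Method | Estimate | 95% limits |
|---|---|---|
| One-sample HL, percent reduction | 26.9% | 3.8 to 49.2 |
| Layout B (zeros) | 26.2% | 7.7 to 49.2 |
| Layout A (unpaired counts) | 4.7 events | −6.5 to 19.5 |
| Paired HL on counts, for comparison | 4.8 events | 2.1 to 11.5 |

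**The case against.** The strongest defence is that SAP 2.5.2 defines the target clearly and SAP 5.4.1 only names software. SAP section 1 leaves programming detail to separate specifications that are not available here, and a result in events would visibly miss the definition. A careful programmer could use layout B, which keeps the pairing and the percent unit. Its point estimate, the sample median, is the summary measure that the estimand names. The Hodges-Lehmann value is an accompanying estimate, since the test runs in PROC UNIVARIATE and SAP 2.5.2 separately asks for the descriptive median and quartiles of percent reduction.

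Much of this stands. A reader might infer that the counts have to be entered as two groups, so that the report will show events with an interval that is too wide. The documents do not support that: no layout is specified, layout B exists, and even under layout A the widths agree when baseline and treatment counts are uncorrelated. The planned baseline categories, from below 7 to 22 or more events, make positive correlation likely but do not establish it. A reader might also infer that the primary test is compromised; it is not.

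The defence does not rescue the sentence. Layout B is not a Hodges-Lehmann estimate of one sample, and its nominal 95% interval covers about 88%. Unseen specifications cannot be assumed to override the SAP.

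**Conclusion.** The sentence in SAP 5.4.1 is wrong as written: it pairs a one-sample estimate with a two-group procedure, and neither workable layout gives the estimate and interval that SAP 2.5.2 promises. The direction of the interval error depends on the layout. It is about 0.96 to 1.8 times the paired width under layout A, given the assumed rates and variation, and too narrow under layout B. These figures are a range under stated assumptions, not a forecast.

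The same method is called for in the COVID-19 sensitivity analysis (SAP 2.5.5) and for acute priapic events (SAP 2.6.2), and no other procedure is named for them. A link to the success decision should not be inferred. SAP 2.5.2 also requires a reduction of at least 25% but does not say which estimate is meant, and SAP 5.4.1 does not say which estimate is pooled over the imputed datasets. The mismatch would reach those steps only if the Hodges-Lehmann value is the one used. It should be corrected before analysis, as a matter of specification.

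**What to change.** Replace the sentence in SAP 5.4.1 with:

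> The Hodges-Lehmann estimate is the median of all pairwise (Walsh) averages of the subject-level percent reductions, with the 95% CI obtained by inverting the one-sample Wilcoxon signed-rank test.

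Name the code that produces it, and refer to it from SAP 2.5.5 (COVID-19 analysis) and SAP 2.6.2. Where SAP 2.6.2 asks for a median change in acute events, the averages are taken over subject-level changes. The cost is one SAP sentence and a short macro. No data collection, sample size or test changes.

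### The tipping-point definition and stop value name only p > 0.05, omit the 25% limb of the success rule, and conflict with step 4's own continuation clause

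*SAP*

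**What the plan says.** - **Success rule (SAP 2.5.2).** "The study would be declared a success, if percentage reduction in events is $\geq 25\%$ and $p < 0.05$ is obtained from" the signed-rank test. Both conditions are needed.
- **Hypotheses (SAP 2.5.2).** The null is H0: p < 0.25, "where p is the percent reduction in priapic events by 26 weeks".
- **Purpose (SAP 2.5.5, Protocol 12.4.4).** The search looks for the delta at which the trial's conclusion flips. SAP 2.5.5 adds that it is run only if a significant number of data are missing.
- **Definition (SAP 5.4.1).** "The tipping point is the delta value which will cause the primary endpoint to be no longer statistically significant".
- **General search rule (SAP 5.4.1).** "If not, a larger delta is chosen and the process will be repeated until the conclusion is overturned".
- **Step 4, continuation (SAP 5.4.1).** "If the combined results does not change the conclusion (i.e., if percentage reduction in events is $\geq 25\%$ statistically significant"; in that case a larger delta is chosen.
- **Step 4, stop (SAP 5.4.1).** The steps repeat "until the tipping point is found", with p > 0.05 given in brackets as the stop value.
- **Test (SAP 5.4.1).** PROC UNIVARIATE is named for the signed-rank test, without a null value.

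**The concern.** The definition and the stop value name one limb of a two-limb success rule. The general search rule, the stated purpose and step 4's continuation clause all follow the overall conclusion, which includes the 25% limb. The instructions disagree when the estimate has dropped below 25% while p is still below 0.05. In that state the trial has failed under SAP 2.5.2, but by the definition it has not yet tipped. Two programmers could report different deltas from the same data. Reading the definition literally gives the later delta, so success would look less sensitive to missing data than it is.

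**Working it through.** **1. Logic of the rule.** Suppose that at some delta the pooled estimate is 22% and p = 0.01.
- Success rule: failed, since 22% < 25%.
- Continuation clause: not met, so no larger delta is chosen.
- Definition and stop value: not met, since p < 0.05, so the tipping point has not been found.

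The procedure has no defined next step.

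**2. Can that state occur? Start from the plan's own sample size.** SAP section 3 gives 34 evaluable subjects, a baseline of 10.0, a 25% reduction (difference 2.5), an SD of the difference of 5.0 and two-sided alpha 0.05.
- Standard error = 5/√34 = 0.8575; noncentrality = 2.5/0.8575 = 2.92; df = 33.
- One-sample t power against zero is 80.8% (79.5% at n = 33). Signed-rank simulation gives 79.1% (normal differences) and 80.0% (Poisson differences).
- 34/0.95 = 35.8, so 36 enrolled.

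The stated figure reproduces against a null of zero. Against a 25% null with a true 25% reduction, the rejection rate is only 4.5%.

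The smallest mean difference significant against zero is 2.0345 × 0.8575 = 1.74 of 10, or 17.4%. So if p is against zero, a mean reduction between about 17% and 25% is significant and still fails the success rule.

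**3. Which limb fails first?** The 17.4% figure assumes a uniform shift. Delta is added only to imputed counts, which creates a few extreme values, so the order has to be simulated.

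Set-up: 36 subjects; gamma-Poisson baseline counts with at least 3 events in 12 weeks, scaled by 26/12; Poisson imputation at the observed effect; integer deltas up to 30. Only trials meeting both limbs at delta 0 were followed, from 60 simulated per setting. The numbers imputed, the true reductions other than 25% and the spreads other than SD 5 are assumptions.

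Zero null, SD of the difference about 5, 7 of 36 imputed, Hodges-Lehmann estimate (gap = delta for p minus delta for the estimate):

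| True reduction | Initially successful | 25% limb first | p first | Tie | Median gap |
|---|---|---|---|---|---|
| 25% | 34 | 31 | 2 | 1 | 3 |
| 30% | 52 | 44 | 7 | 1 | 3 |
| 40% | 60 | 25 | 32 | 3 | −7.5 |
| 50% | 60 | 5 | 54 | 1 | −12.5 |

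- **Second check, 6 of 36 imputed, zero null.** The 25% limb failed first in 21/25 trials at a true 25% (median gap about 4), 7/25 at 35% and 0/25 at 50%.
- **Spread, 7 imputed, true 25% and 30%.** At SD about 3.2 the 25% limb failed first in 36/36 and 46/52 (gaps 6 and 5.5). At SD about 7.7 it did so in 28/47 and 30/50 (gap 1 in both).
- **Rubin-pooled run, higher spread, 9 imputed.** 98/110 at 25%, 98/133 at 35%, 34/150 at 50%. The order at 35% therefore depends on the set-up.
- **Sample median in place of Hodges-Lehmann, SD about 5, 7 imputed.** 25/41 at 25% and 26/54 at 30%, so the order is less one-sided.
- **2 of 36 imputed, SD about 5.** Neither limb failed by delta 30 in 28/39, 38/56, 57/58 and 60/60 trials at 25%, 30%, 40% and 50%.
- **25% null.** The estimate fell below 25% before p exceeded 0.05 in no trial in any setting. This is expected: in a single completed dataset, a signed-rank result significantly above 25% already implies a Hodges-Lehmann estimate above 25%.

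**The case against.** A reader might infer that the search ignores the 25% limb altogether. It does not: step 4's continuation clause contains it, and the general rule and SAP 2.5.5 both refer to the conclusion as a whole. On this view the definition and the bracketed stop value are loose wording that a careful programmer would read in context. That is a fair description of the defect, which is an internal inconsistency. It still matters, because the only sentence that defines the tipping point uses p alone.

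A reader might also infer that the 25% limb is generally lost first, so that the reported delta always overstates robustness. The documents do not support that. SAP 2.5.2 writes the null at 25%, and under that null p > 0.05 is never the later failure. A zero null is an inference from the sample size, and from the fact that a separate 25% limb would be largely redundant if p already tested 25%. Even against zero, the order reverses at larger effects.

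Finally, the analysis may hardly be exercised. The primary set is 26-week completers and planned dropout is 5% (36 × 0.05 = 1.8, about 2 subjects), where most simulated trials tip on neither limb. This stands in part. SAP 2.5.3 also discards and imputes data after a change of background or prophylactic therapy, so completers can contribute imputed data.

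**Conclusion.** The inconsistency is certain from the text: the definition and stop value leave out the 25% limb that the success rule and step 4's continuation clause include.

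Its numerical effect is conditional. If the test is against zero, the true reduction is near 25–30%, about 6–7 of 36 subjects are imputed and the estimate is Hodges-Lehmann, the 25% limb usually fails first. The p-only delta is then later by a median of roughly 3–4 events at SD about 5 (about 1 to 6 across the spreads tried), and robustness is overstated. A near-threshold success is also where the tipping point is most informative. Outside those conditions the p-only rule often gives the same answer or the search finds no tipping point, so a general claim of overstated robustness would go too far. Each setting had 25 to 150 trials, so the counts are approximate.

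Severity is minor to moderate. This is a sensitivity analysis, run only if missing data are judged significant in number, and it does not alter the primary estimate, p-value or success decision.

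**What to change.** In SAP 5.4.1:
- Define the tipping point as the smallest delta at which either limb of the SAP 2.5.2 success rule fails.
- Replace the bracketed stop value in step 4 with the same condition.
- Report both deltas: the first with the estimate below 25% and the first with p > 0.05. For the second, the grid has to continue past the first failure.
- State the null value of the signed-rank test, so that the p-value in the rule is unambiguous.

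The cost is two amended sentences plus one stating the null, with no new data. Where p fails first, the reported tipping point does not change.
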